5.2 Study Duration

Potential participants must be willing to participate in a study that involves four, 5-hour sessions over the course of 2-3 weeks.

We anticipate being able to enroll three participants per month and complete all study procedures, including data analysis within 18 months.

5.3 Use of radiation: NA

5.4 Use of Center for Magnetic Resonance Research: NA

6.0 Data and Specimen Banking

MEDICAL PROTOCOL (HRP-590)**PROTOCOL TITLE: Sugars Project****VERSION DATE: 22 FEB 2023****6.1 Storage and Access**

Cigarette butts and biomarker specimens will be collected and stored at the study site (University of Minnesota - Tobacco Research Programs, [name]) until delivery to the Masonic Cancer Center's [name] laboratory for storage and analysis. Samples that are not used for the primary analysis of study biomarkers will be banked for future use. The banked samples will be stored until analyses and destroyed if it is determined they are no longer needed. The samples, which may also include DNA or RNA, may be stored up to a maximum of 10 years from the study's end. A subject has the right to withdraw consent at any time by informing the Principal Investigator by following the instructions provided in the consent and HIPAA documents. If this occurs, any remaining identifiable research sample(s) will be destroyed.

6.2 Data

Data will be stored in a secure database (RedCap) and on University of Minnesota servers. Only study personnel directly involved with the study will have access to the linked records. The samples that will be transferred to the laboratory or stored for future analyses will be de-identified. We will not be transferring data that has any identifying information over the internet.

Biomarker samples (buccal cells) that are banked after the completion of the primary analyses will be stored at the Masonic Cancer Center [name] laboratory located at the Cancer and Cardiovascular Research Building for future use.

6.3 Release/Sharing

No identifying information will be shared with outside investigators. If used in any collaborative efforts beyond the scope of this study, any shared data will be de-identified. However, records for the study may be reviewed by departments at the University with appropriate regulatory oversight. The records may also be reviewed by a representative of the funding agency, National Institutes of Health, and the Food and Drug Administration.

7.0 Sharing of Results with Participants**7.1 Sharing of genetic testing**

Information will not be shared with participants.

8.0 Study Population**8.1 Inclusion Criteria:**

- a) Male or female age 21 years or older;
- b) Must smoke at least 5 cigarettes/day for at least 1 year (confirmed by CO >10 ppm or NicCheck test of 6 or greater);

MEDICAL PROTOCOL (HRP-590)

PROTOCOL TITLE: Sugars Project

VERSION DATE: 22 FEB 2023

- c) Smoking cigarettes that have been evaluated to have medium levels of sugar content;
- d) No quit attempts in the past month nor intentions to quit smoking in the next month;
- e) Participants are in good physical health (no unstable medical conditions) as determined by the licensed medical professional;
- f) Participants are in stable, good mental health (e.g. not currently, within the past 6 months, experiencing unstable or untreated psychiatric diagnosis) as determined by the licensed medical professional;
- g) Stable vitals sign measurements (systolic BP \leq 160 and >90 mmHg, diastolic BP \leq 100 and >50 mmHg and heart rate \leq 105 and >45 bpm) as determined by the licensed medical professional
 - a. Participants failing for vital signs will be allowed to re-screen once;
- h) Participants must be able to read for comprehension or completion of study documents (confirmed during informed consent process);
- i) Participants have provided written informed consent to participate in the study.

8.2 Exclusion Criteria:

- a) Significant immune system disorders, respiratory diseases, kidney or liver diseases or any other medical disorders that may affect biomarker data as determined by the licensed medical professional;
- b) Current or recent alcohol or drug abuse problems or use of substances of abuse (other than marijuana) in the past month;
- c) Tobacco use other than cigarettes or marijuana for >9 days per month
- d) Current use (within past 2 weeks) of nicotine replacement or other tobacco cessation products;
- e) Women who are pregnant or nursing or planning to become pregnant.
- f) Frequent marijuana use. Quantified as >9 days of marijuana use in the last 30 days

8.3 Screening

Participants who agree to go through the pre- screening process will be assigned a screening number and taken through a screening questionnaire. Participants who meet the eligibility criteria described in section 8.1 and 8.2 will be asked to complete a more thorough screening visit, where the entire study will be explained in detail, informed consent will be obtained and the screening measures will be completed. The format for this visit will either be done in-person in the clinic or remotely via a secured-video conferencing link. In either scenario, participants will sign an e-consent.

9.0 Vulnerable Populations

MEDICAL PROTOCOL (HRP-590)

PROTOCOL TITLE: Sugars Project

VERSION DATE: 22 FEB 2023

9.1 Vulnerable Populations

No vulnerable populations will be used in the study.

10.0 Local Number of Participants

10.1 Local Number of Participants to be Consented

Up to 75 smokers will be consented in order to get 30 completers.

11.0 Local Recruitment Methods

11.1 Recruitment Process

We will recruit up to 75 adult smokers (30 completers) from the Minneapolis-St. Paul metro area who smoke at least 5 cigarettes per day. Smokers will be recruited through the University of Minnesota Tobacco Research Programs. A variety of media will be used that will foster the recruitment across a spectrum of age, education and socioeconomic status, and race/ethnicity.

11.2 Identification of Potential Participants

Participants will be recruited through various media (internet, television, newspaper, radio). Smokers will contact our clinic and be screened for eligibility over the telephone. During this screening, we will maximize retention of the participants between the screening and clinic visits by covering transportation costs and compensating them for their time. We will provide a respectful environment for the subject and train personnel on methods for minimizing subject dropouts.

11.3 Recruitment Materials

Participants will be recruited through printed flyers and advertisements through a variety of media outlets and the internet, including but not limited to, Facebook, newspapers, radio, and television ads.

11.4 Payment

Payment will be made using the Greenphire Clincard. Participants will be paid \$25 for the screening visit and \$25 for the baseline visit (\$10 for transportation reimbursement, \$15 for the study visit). Eligible participants will be paid \$75 for each of the clinic visits (\$10 for transportation reimbursement, \$65 for the study visit x 4 visits = \$300). Additionally, participants may earn up to an additional \$5 each study visit based on the MCP questionnaire. At the end of the study, participants will be paid a \$75 bonus for completing all sessions. The maximum total amount a participant will be paid is \$445.

12.0 Withdrawal of Participants

12.1 Withdrawal Circumstances

MEDICAL PROTOCOL (HRP-590)

PROTOCOL TITLE: Sugars Project

VERSION DATE: 22 FEB 2023

A study participant may be discontinued from the study if investigators determine that this is the best decision in order to protect his/her safety. In the event that a participant either withdraws from the study or the investigators decide to discontinue a participant due to an adverse event (AE) or serious adverse event (SAE), the participant will have appropriate follow-up assessments and if necessary, referrals will be made for medical care. The participant experiencing an AE/SAE will be followed until the problem resolves, stabilizes, or is clearly unrelated to the study product. Any AE that remains open will be reviewed and closed at the last study visit.

12.2 Withdrawal Procedures

Subject will be informed about the withdrawal at the visit and data collection will stop.

12.3 Termination Procedures

No additional procedures will be conducted if participants are withdrawn.

13.0 Risks to Participants

13.1 Foreseeable Risks

The potential risks for participants recruited for this study are minimal. Potential risks for all participants include: emotional discomfort, breach of confidentiality, risks associated with smoking, risks to fetuses, and changes in blood pressure/heart rate.

Survey Questionnaires. The interviews will include questions about medical history, drug and alcohol use, and questionnaires about mood. Answering these personal questions could make the subject feel uncomfortable.

Risk of breach of confidentiality. There is always a small risk of breach of confidentiality. All subject samples and case report forms will be labeled with a unique numerical identifier in place of direct identifiers. The link between a participant and this unique identifier, and any other computer files containing direct identifiers will be kept in a password-protected file on a locked computer. Only the PI, study staff, and possibly approved regulatory officials (as required by the policies of the University of Minnesota and federal agencies such as the NIH, NCI, or FDA) will have access to direct identifiers. Case report forms with direct identifiers, demographic information and medical history will be kept separately and securely at all times.

Smoking Cigarettes. All cigarettes are detrimental to a person's health and can lead to severe or fatal medical problems including:

- a. Cardiovascular Diseases: Coronary heart disease, heart attack, stroke, peripheral vascular disease, reduced blood circulation, abdominal aortic aneurysm
- b. Respiratory Diseases: Emphysema, bronchitis, tuberculosis and chronic airway obstruction
- c. Cancers: Lung, bladder, liver, colon, cervical, esophageal, kidney, larynx, mouth, pancreatic, throat, stomach cancers and acute myeloid leukemia

MEDICAL PROTOCOL (HRP-590)

PROTOCOL TITLE: Sugars Project

VERSION DATE: 22 FEB 2023

- d. Diabetes
- e. Immune function, rheumatoid arthritis
- f. Other Health Risks Associated with Smoking: Including but not limited to infertility, ectopic pregnancy, lower bone density in postmenopausal women, hip fracture in women, male sexual dysfunction; age-related macular degeneration, blindness and cataracts

Study Cigarettes. The levels of sugar that will be added to study cigarettes will be no higher than those found in most popular cigarette brands. There is no additional risk to participants by using the study cigarettes.

At the end of the trial, participants will be strongly encouraged to stop use of all tobacco products and to set a quit date, and if requested, we will provide treatment resources and referral to different treatments including the state quit line.

Participants will be under medical supervision throughout their study participation and adverse symptoms will be recorded and monitored by the project PI, [name] along with the study licensed medical professional.

13.2 Reproduction Risks

Pregnant women will not be recruited. If participants choose to be sexually active, they should use an appropriate “double barrier” method of birth control (such as female use of a diaphragm, intrauterine device (IUD), or contraceptive sponge, in addition to male use of a condom) or the female should be using prescribed “birth control” pills, injections, or implants. Female participants with child-bearing potential will be tested for pregnancy at the screening visit. If a participant becomes pregnant during the study, she will be withdrawn from the study. Approximately 30 days after being withdrawn or having a positive pregnancy test, the research staff will call the participant to confirm her due date. The licensed medical professional will follow-up with the participant after delivery to ask questions about the baby’s health. A separate consent form will be signed in order to obtain data from pregnant participants.

13.3 Risks to Others

NA

14.0 Potential Benefits to Participants

14.1 Potential Benefits

Whereas no assurance can be made to an individual subject that he/she will personally benefit from such research, the experience should not impose any significant risk. Participants will have the opportunity to learn about factors that may be associated with tobacco use. Quitting tobacco will be strongly recommended to our participants and cessation materials will be provided if requested. Referrals to community resources can also be made.

15.0 Statistical Considerations

15.1 Data Analysis Plan

Trial design

The aim of this study is investigate the impact of sugar content in cigarette tobacco on cigarette abuse liability and appeal. The hypothesis is that the collected measures will indicate lower abuse liability for cigarettes with lowest sugar content.

This is a within-subject crossover study design with multiple periods and multiple treatments. The orders of the 3 sugar levels are counterbalanced using a Latin square, which will be created in advance by an independent statistician.

Trial endpoints

Outcome measures include subjective responses to cigarettes, behavioral measures, and mouth-level nicotine exposure.

Two *primary* outcome measures, which were used for power/sample size determination, include (1) the satisfaction of the Modified Cigarette Evaluation Questionnaire (mCEQ) and (2) the crossover point from the Multiple Choice Procedure task.

The other subjective and behavioral outcomes and mouth-level nicotine exposure will be *secondary*.

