5.0 Procedures Involved

5.1 Study Design

Overview: Participants (N=30 completers) will complete a baseline visit where they will smoke their usual brand cigarette. In the next three sessions, they will receive one of three study cigarettes with varying sugar content (low, medium and high) in a double-blind manner and counterbalanced order across participants. In each session, participants will first smoke either their usual brand cigarettes (at baseline) or their assigned study cigarette (subsequent sessions) in a regimented manner: 10 puffs total, 30 seconds between puffs. There will be a one-hour interval since the time of cigarette extinction before smoking the next cigarette. After this interval, participants will smoke their assigned cigarette *ad libitum* within a 10 minute time period. Safety and subjective measures will take place during this session as described below.

Anticipating a 60-65% attrition rate based on current experiences, we will recruit up to 75 participants.

Study Procedures: Smokers who smoke at least 5 cigarettes/day will attend 4 laboratory sessions during which they will be asked to smoke their usual brand (UB) cigarettes and then one of three study cigarettes with low, medium and high levels of sugar in separate sessions using a within-subject design with conditions counterbalanced determined by a Latin square. In each session, smokers will be asked to smoke a cigarette in a standardized manner (10 puffs, 30 second interval between puffs) and 1 hour later, *ad libitum*. Each of the sessions will be separated by at least 48 hours but not more than 5 days. The proposed study design has been used to assess the abuse liability of electronic cigarettes compared to other tobacco/nicotine products,⁹⁹⁻¹⁰¹ that vary in flavors and modified risk claims,¹⁰² and that vary in menthol

MEDICAL PROTOCOL (HRP-590)

[figure not shown]
PROTOCOL TITLE: Sugars Project

VERSION DATE: 22 FEB 2023

concentration and nicotine dose.¹⁰³ This design is also being utilized to determine the abuse liability of flavored cigar products.¹⁰⁴

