The first session for all participants will involve smoking their UB cigarettes. Participants will be asked to refrain from smoking for at least 12 hours prior to each session and must have alveolar CO ≤ 10 ppm to qualify for the session. Subsequently, the IVR records will be examined and vitals (blood pressure and heart rate) will be assessed through an automated cuff to ensure that eligibility criteria are still met. After a 30-minute rest period, participants will complete the MNWS, submit an alveolar CO sample, and will smoke their UB cigarettes in a regimented manner (10 puffs total, 30 seconds between puffs). Five minutes after extinguishing the cigarette, another CO measurement will be taken and participants will be asked to complete the mCEQ, Drug Effects/Liking Questionnaire, MNWS, QSU and Sensory Effects of Smoking Questionnaire, in a specified order via REDCap. The spent cigarette filter will be collected for nicotine analysis. There will be a one- hour interval since the time of cigarette extinction before smoking the next cigarette. During the intervening times between cigarettes, smokers will be allowed to read magazines, listen to neutral podcasts, or watch neutral videos. After this interval, participants will submit another CO, complete the MNWS and smoke their UB cigarettes *ad libitum* within a 10-minute timeframe and the same testing procedures will be followed. Twenty minutes after the second cigarette, the Perceived Health Risk Questionnaire will be administered and then at 30 minutes the Cigarette Purchase Task and Multiple Choice Procedures for the UB cigarettes will be administered. At 50 minutes (2 hours after smoking the first cigarette), participants will be asked to rinse their mouths and oral cells will be collected. At the very end of the session, the Willingness to Switch questionnaire will be administered. Once the Willingness to Switch questionnaire has been completed a number will randomly be selected from the Multiple Choice Procedures task. This will be done by pulling a number 1- 16 out of a jar. The participants will receive either an additional cigarette or the money associated with that number, depending on which choice was made for that number. The participant may choose to smoke the cigarette or not.

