15.2 Power Analysis

A total of 30 completed participants will achieve >80% power, for each of the two primary outcomes (satisfaction and crossover point), to detect two sugar conditions (high vs. low)’ difference of a moderate effect size ($d = 0.6$, the target scenario) at a 0.025 (= 0.05/2 primary outcomes) significance level, assuming a moderate correlation between sessions ($r = 0.50$) based on a T^2 test using PASS14 (NLSS, 2015). A total of up to 75 eligible smokers will be enrolled..

We note that because of the uncertainty of the effects of sugars and the range of effect sizes, we chose an effect size that is more conservative but near the range of the effect sizes (based on the endpoint of crossover point from the Multiple Choice Procedure task) used in most studies. The powers of the target scenario and other scenarios by changing the within-subject correlation and effect size, with the fixed sample size ($n = 30$) and type I error ($\alpha = 0.025$), are presented in the table below. We note that the actual power for the factor of sugar level could be larger since 3 sugar levels will be studied.

Scenario	Power	Effect size (d)	Within-subject correlation (r)
Target scenario	0.81	0.6	0.5
	0.89	0.6	0.6
	0.64	0.5	0.5

Other scenarios	0.75	0.5	0.6
	0.92	0.7	0.5
	0.96	0.7	0.6

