15.3 Statistical Analysis

General Approach

All statistical analyses will be performed using SAS or R. All statistical tests will be two-tailed. A Bonferroni adjustment will be used to account for 2 primary endpoints ($p < 0.025$ considered significant). Analyses of the secondary endpoints will not be adjusted ($p < 0.05$ considered significant). Proper transformation such as the logarithm transformation will be used to approximate normality for the outcome variables.

Describing the Study Population

Baseline characteristics of the participants will be summarized using mean and standard deviation (SD) for continuous variables and frequency and percentage for categorical variables.

Primary Analysis

The primary data analysis method will be linear mixed models including the two within-subject factors, sugar condition (2 dummy variables for the medium and high sugar levels) and time (2 dummies for the 3rd and 4th sessions), adjusted for the nicotine levels in spent filters of the first study cigarette used in each of the laboratory sessions (under the fixed puffing pattern). The potential carry-over effect will be tested by including the previous session's condition, i.e., 2 dummies for the previous session being medium and high sugar level (Diggle et al., 2002, p150-153). Note that the usual brand's measure (collected at the 1st session) and other participant-level factors are naturally adjusted across different sugar conditions because of the within-subject design, and hence are not included in the model. However, participant-level factors will be examined for any potential moderating effect (i.e., interaction) as an exploratory analysis.

Subgroup Analysis

Subgroup analyses will be performed for female and male smokers. The analyses will follow the same approach described for the overall group. Note that this study is not powered for detecting the potential interaction of gender and sugar level, however, we will report the size and significance of the interaction together with the subgroup analysis results to provide information for understanding of the role of gender.

Missing data

Every effort will be made to limit the amount of missing data in this trial, and study participants will be incentivized to attend study sessions. We anticipate a high retention rate (>80%) because of the short period of time of this laboratory study.

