We will compare subjects who do and do not complete the study sessions in terms of their baseline characteristics. All observed data will be utilized in the analyses, with missing data being assumed to be missing at random, by using the mixed effects models.

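### If the Latin square means three orders, the planned carry-over check is very weak; using all six orders strengthens it at no cost in participants or primary-model precision

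*Combined protocol and SAP*

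**What the plan says.** Section 5.1 describes a "within-subject design with conditions counterbalanced determined by a Latin square", and Section 15.1 repeats that "The orders of the 3 sugar levels are counterbalanced using a Latin square", prepared in advance by an independent statistician. No section lists the sequences, says how many there are, or requires each level to follow each other level equally often.

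Section 5.1 also fixes the start of every sequence: "The first session for all participants will involve smoking their UB cigarettes". On spacing it says: "Each of the sessions will be separated by at least 48 hours but not more than 5 days".

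Section 15.3 specifies a linear mixed model with sugar condition, session and spent-filter nicotine. It adds a test for carry-over using "2 dummies for the previous session being medium and high sugar level". It gives no expected carry-over size and no rule for keeping or dropping those terms. The power statement in Section 15.2 concerns only the high-low comparison.

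**The concern.** One 3×3 Latin square on low (L), medium (M) and high (H) gives the orders LMH, MHL, HLM, or the mirror set LHM, HML, MLH. In the first set, M is only ever preceded by L, H by M, and L by H. In the second and third study sessions, knowing the current cigarette therefore tells you the previous one. The first study session follows usual brand for everyone, so it alone has no study-cigarette predecessor, and it is the only place where direct and carry-over effects come apart. The carry-over terms can be estimated, but poorly.

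A non-significant result from such a check would give little reassurance. If carry-over did appear, adjusting for it would cost most of the trial's power. With all six orders, each level is preceded by both of the others, and this near-confounding goes away.

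**Working it through.** **Inputs.** From Section 15.2: 30 completers, target d = 0.6, r = 0.5 (0.6 also tabulated), alpha 0.025 per primary outcome. From Section 15.3: two-sided tests, two session dummies, two sugar dummies, two previous-condition dummies. Assumed, because the documents do not say: three orders for the literal reading; alpha 0.05 for the carry-over test; carry-over linear in sugar level, with a high-low size of 0.3, 0.6 or 0.9 SD. Total SD is 1, so the residual variance is σ² = 1 − r. The spent-filter nicotine covariate is left out because the documents give no values for it.

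**The plan's own power first.** For a paired comparison the noncentrality is d√30 / √(2(1 − r)) on 29 df. At d = 0.6, r = 0.5 this is 0.6 × 5.477 / 1 = 3.29, giving power 0.816 (stated 0.81). The other five scenarios give 0.898, 0.647, 0.754, 0.923 and 0.968 (stated 0.89, 0.64, 0.75, 0.92, 0.96). The table reproduces to within 0.01.

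**Precision under each design.** I formed the information matrix for participant, session and sugar condition, with and without the carry-over dummies. The designs are three orders × 10 and six orders × 5; both versions of the single square give the same results. Treating participant as fixed, the variances in units of σ² are:

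| Quantity (high-low) | Three orders | Six orders |
|---|---|---|
| Sugar effect, no carry-over terms | 2/30 = 0.0667 | 0.0667 |
| Sugar effect, carry-over terms kept | 0.333 | 0.083 |
| Carry-over difference | 0.600 | 0.150 |

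With σ² = 0.5, the SE without carry-over terms is √(0.0667 × 0.5) = 0.183 under both designs. With them it is √(0.333 × 0.5) = 0.408 for three orders and √(0.083 × 0.5) = 0.204 for six. For the carry-over difference it is √(0.600 × 0.5) = 0.548 and √(0.150 × 0.5) = 0.274. A random intercept recovers some between-participant information: 0.374 and 0.203 for the adjusted sugar effect, 0.490 and 0.266 for carry-over.

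**Power at r = 0.5** (noncentral t or F; 54 residual df with carry-over terms, 56 without; ranges run from fixed participant to random intercept):

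| Quantity | Three orders | Six orders |
|---|---|---|
| Planned 2-df carry-over test, 0.3 SD | 0.07-0.08 | 0.14-0.15 |
| Same, 0.6 SD | 0.14-0.17 | 0.46-0.49 |
| Same, 0.9 SD | 0.28-0.34 | 0.82-0.85 |
| Single high-low carry-over contrast, 0.6 SD | 0.19-0.23 | 0.58-0.60 |
| High-low sugar effect, carry-over terms kept, d = 0.6 | 0.21-0.25 | 0.74 |
| High-low sugar effect, no carry-over terms, d = 0.6 | 0.83 | 0.83 |

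At r = 0.6 the carry-over-adjusted power is 0.26-0.30 against 0.83-0.84.

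**Uneven completion.** With 4/6/5/6/4/5 completers over the six orders, the adjusted SE is 0.21 and power 0.71-0.72.

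**Bias of the unadjusted model.** Projecting a carry-over pattern onto the model without carry-over terms gives the bias of the high-low estimate. For a linear carry-over of high-low size c it is −c/3 under both designs. If only one level carries over, by c, it is 0 or ±2c/3 with three orders (depending on the square and the level) and 0 or ±c/3 with six.

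**The case against.** **Three orders is an assumption.** The independent statistician's list is not in the documents and may already use a pair of squares. That stands. If so, the design does not change and one clarifying sentence is enough.

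**Nothing primary is touched.** Section 15.3 does not commit to keeping carry-over terms, so the fall to 0.21-0.25 describes an analysis the plan may never run. That stands too, and the 0.83 for the unadjusted model should be read alongside it.

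**Carry-over may be small.** Sessions are at least 48 hours apart, each follows at least 12 hours without smoking, and each requires CO of 10 ppm or less. Nothing in the documents suggests a carry-over of 0.6 or 0.9 SD. But the plan chose to run the check, and it should be able to inform.

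**The remedy leaves the check modest.** This is true: 0.14-0.15 power at 0.3 SD and 0.46-0.49 at 0.6 SD.

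**Non-completers also contribute.** Up to 75 people may enrol, and the plan says "All observed data will be utilized in the analyses, with missing data being assumed to be missing at random". Partial attenders add first-session data, which is where three orders get their separation. In an assumed extreme case (15 more attend two study sessions and 30 attend one), adjusted power is 0.27-0.52 with three orders and 0.80-0.89 with six. The gap changes in size but not in direction.

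**Conclusion.** The concern holds, on the condition that a single square of three orders is meant. Under that reading the planned carry-over test has about one chance in six of detecting a carry-over as large as the target sugar effect. Even at 0.9 SD it would miss about two times in three. Moving to six orders halves the SE of the carry-over difference (0.548 to 0.274 with participant fixed). It also cuts the variance penalty for adjustment from a factor of 4.20-5.00 to 1.24-1.25.

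The primary model's precision and the plan's stated power do not depend on the choice. Equality of primary precision is exact for balanced completers without the nicotine covariate, and should hold approximately with it. This is a worthwhile improvement to a supporting analysis, not a threat to the primary result.

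**What to change.** In Sections 5.1 and 15.1, replace the Latin-square wording with: all six orders of the three sugar levels (a pair of Latin squares balanced for the preceding condition), with approximately equal allocation, about 5 completers per order. Exact balance among completers is not needed, since the mixed models use all observed data. If six orders are already intended, say so.

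The cost is a different list from the independent statistician. No participants, visits or cigarettes are added.

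If enrolment has begun, apply the six-order list to the remaining allocations. The gain shrinks the later this is done:

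| Completers already on one square | Completers per order | Adjusted high-low power (d = 0.6, r = 0.5) |
|---|---|---|
| 12 of 30 | 7/7/7/3/3/3 | 0.67-0.68 (SE 0.22) |
| 18 of 30 | 8/8/8/2/2/2 | 0.58-0.60 |
| 24 of 30 | 9/9/9/1/1/1 | 0.43-0.46 |

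Each of these is still better than staying with three orders (0.21-0.25).
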